8.4.5.2. Exposure During Breastfeeding

An EDB occurs if:

- A female participant is found to be breastfeeding while receiving or after discontinuing study intervention.

- A female nonparticipant is found to be breastfeeding while being exposed or having been exposed to study intervention (ie, environmental exposure). An example of environmental EDB is a female family member or healthcare provider who reports that she is breastfeeding after having been exposed to the study intervention by ingestion, inhalation, or skin contact.

The investigator must report EDB to Pfizer Safety within 24 hours of the investigator's awareness, irrespective of whether an SAE has occurred. The information must be reported using the CT SAE Report Form. When EDB occurs in the setting of environmental exposure, the exposure information does not pertain to the participant enrolled in the study, so the information is not recorded on a CRF. However, a copy of the completed report is maintained in the investigator site file.

An EDB report is not created when a Pfizer drug specifically approved for use in breastfeeding women (eg, vitamins) is administered in accordance with authorized use. However, if the infant experiences an SAE associated with such a drug, the SAE is reported together with the EDB.

8.4.5.3. Occupational Exposure

The investigator must report any instance of occupational exposure to Pfizer Safety within 24 hours of the investigator's awareness using the CT SAE Report Form regardless of whether there is an associated SAE. Since the information about the occupational exposure does not pertain to a participant enrolled in the study, the information is not recorded on a CRF; however, a copy of the completed report is maintained in the investigator site file.

8.4.6. Cardiovascular and Death Events

Not applicable.

8.4.7. Disease-Related Events and/or Disease-Related Outcomes Not Qualifying as AEs or SAEs

Not applicable.

8.4.8. Adverse Events of Special Interest

Not applicable.

8.4.8.1. Lack of Efficacy

This section is not applicable because efficacy is not expected in the study population.

8.4.9. Medical Device Deficiencies

Not applicable.

8.4.10. Medication Errors

Medication errors may result from the administration or consumption of the study intervention by the wrong participant, or at the wrong time, or at the wrong dosage strength.

Medication errors are recorded and reported as follows:

Recorded on the Medication Error Page of the CRF	Recorded on the Adverse Event Page of the CRF	Reported on the CT SAE Report Form to Pfizer Safety Within 24 Hours of Awareness
All (regardless of whether associated with an AE)	Any AE or SAE associated with the medication error	Only if associated with an SAE

Medication errors include:

- Medication errors involving participant exposure to the study intervention;
- Potential medication errors or uses outside of what is foreseen in the protocol that do or do not involve the study participant.

Other examples include, but are not limited to:

- The administration of expired study intervention;
- The administration of an incorrect study intervention;
- The administration of an incorrect dosage;
- The administration of study intervention that has undergone temperature excursion from the specified storage range, unless it is determined by the sponsor that the study intervention under question is acceptable for use.

Whether or not the medication error is accompanied by an AE, as determined by the investigator, such medication errors occurring to a study participant are recorded on the medication error page of the CRF, which is a specific version of the AE page and, if applicable, any associated serious and nonserious AE(s), are recorded on the AE page of the CRF.

In the event of a medication dosing error, the sponsor should be notified within 24 hours. Medication errors should be reported to Pfizer Safety within 24 hours on a CT SAE Report Form **only when associated with an SAE**.

8.5. Pharmacokinetics

Whole Blood samples (approximately 3 mL) to provide approximately of 1 mL plasma, will be collected for measurement of plasma concentrations of sisunatovir as specified in the [SoA](#). A whole blood aliquot (approximately 200 μ L) from the PK blood draw only will be collected for in vivo blood/plasma ratio assessment on Day 4 and time points as specified in the [SoA](#). Exploratory micro-sampling PK samples for the measurement of sisunatovir concentrations will be collected, in order to evaluate micro-sampling approach using the

Tasso® device. Total blood volume for micro-sampling PK will not exceed 0.1 mL at each time point specified in the [SoA](#). Instructions for the collection and handling of biological samples will be provided in the laboratory manual or by the sponsor. The actual date and time (24-hour clock time) of each sample will be recorded.

The actual times may change, but the number of samples will remain the same. All efforts will be made to obtain the samples at the exact nominal time relative to dosing. Collection of samples up to and including 10 hours after dose administration that are obtained within 10% of the nominal time relative to dosing (eg, within 6 minutes of a 60-minute sample) will not be captured as a protocol deviation, as long as the exact time of the collection is noted on the source document and the CRF. Collection of samples more than 10 hours after dose administration that are obtained \leq 1 hour away from the nominal time relative to dosing will not be captured as a protocol deviation, as long as the exact time of the collection is noted on the source document and the CRF. This protocol deviation window does not apply to samples to be collected more than 10 hours after dose administration at outpatient/follow-up visits with visit windows.

Samples will be used to evaluate the PK of sisunatovir. Samples collected for analyses of sisunatovir plasma concentration may also be used to evaluate safety or efficacy aspects related to concerns arising during or after the study, for metabolite identification and/or evaluation of the bioanalytical method. The data may be used for internal exploratory purposes. The exploratory results may not be reported in the CSR.

Genetic analyses will not be performed on these PK samples. Participant confidentiality will be maintained.

Samples collected for measurement of plasma concentrations of sisunatovir will be analyzed using a validated analytical method in compliance with applicable SOPs.

The PK samples must be processed and shipped as indicated in the instructions provided to the investigator site to maintain sample integrity. Any deviations from the PK sample handling procedure (eg, sample collection and processing steps, interim storage or shipping conditions), including any actions taken, must be documented and reported to the sponsor. On a case-by-case basis, the sponsor may make a determination as to whether sample integrity has been compromised.

Any changes in the timing or addition of time points for any planned study assessments must be documented and approved by the relevant study team member and then archived in the sponsor and site study files, but will not constitute a protocol amendment. The IRB/EC will be informed of any safety issues that require alteration of the safety monitoring scheme or amendment of the ICD.

8.6. Genetics

8.6.1. Specified Genetics

Specified genetic analyses are not evaluated in this study.

8.6.2. Retained Research Samples for Genetics

Retained research samples for genetics will not be collected for this study.

8.7. Biomarkers

Biomarkers are not evaluated in this study.

8.8. Immunogenicity Assessments

Immunogenicity assessments are not included in this study.

8.9. Health Economics

Health economics/medical resource utilization and health economics parameters are not evaluated in this study.

9. STATISTICAL CONSIDERATIONS

Detailed methodology for summary and statistical analyses of the data collected in this study is outlined here and further detailed in the SAP, which will be maintained by the sponsor. The SAP may modify what is outlined in the protocol where appropriate; however, any major modifications of the primary endpoint definitions or their analyses will also be reflected in a protocol amendment.

9.1. Statistical Hypotheses

There is no statistical hypothesis for this study.

9.2. Analysis Sets

For purposes of analysis, the following analysis sets are defined:

Participant Analysis Set	Description
Enrolled	“Enrolled” means a participant’s, or their legally authorized representative’s, agreement to participate in a clinical study following completion of the informed consent process and assignment to study intervention.
PK Concentration Analysis Set	The PK concentration analysis set is defined as all participants who take at least 1 dose of study intervention and in whom at least 1 plasma concentration value is reported.
PK Parameter Analysis Set	The PK parameter analysis set is defined as all participants who take at least 1 dose of study intervention and have at least 1 of the PK parameters of interest calculated.
Safety analysis set	All participants who take at least 1 dose of study intervention.

9.3. Statistical Analyses

The SAP will be developed and finalized before database lock and will describe the analyses and procedures for accounting for missing, unused, and spurious data. This section is a summary of the planned statistical analyses of the primary and secondary endpoints.

9.3.1. Pharmacokinetic Analyses

9.3.1.1. Statistical Methods for Pharmacokinetic Data

The plasma PK parameters of sisunatovir will be listed and descriptively summarized by study day. For AUC_{last} , AUC_{inf} , AUC_{tau} , and C_{max} , box and whisker plots for individual participant parameters overlaid with geometric means will be plotted. The PK parameter analysis set will be used.

The plasma concentrations of sisunatovir will be listed and descriptively summarized by study day and nominal PK sampling times. Individual participant and summary profiles (mean and median plots) of the plasma concentration-time data will be plotted using actual and nominal sampling times, respectively. The PK concentration analysis set will be used.

Concentrations of sisunatovir obtained via microsampling from paired samples compared to plasma sampling will be summarized by sampling time on Day 4 and be listed if possible.

Additional specifications about the tables, listings, and figures will be outlined in the SAP.

9.3.1.2. Derivation of Pharmacokinetic Parameters Prior to Analysis

The plasma PK parameters for sisunatovir, following single dose in a fasted state and repeated twice daily doses in a fed state, will be derived from the plasma concentration-time profiles as detailed in Table 4, as data permit. Actual PK sampling times will be used in the derivation of PK parameters. In the case that actual PK sampling times are not available, nominal PK sampling times will be used in the derivation of PK parameters.

Table 4. Plasma PK Parameters for Sisunatovir

[figure not shown]
Parameter	Study Day	Definition	Method of Determination
C_{max}	1, 4, 8	Maximum observed concentration	Observed directly from data
T_{max}	1, 4, 8	Time to reach maximum concentration	Observed directly from data
AUC_{inf}^a	1, 8	Area under the concentration-time curve from time 0 to infinity	$AUC_{last} + (C_{last}/k_{el})$, where C_{last} is the predicted plasma concentration at the last quantifiable time point estimated from the log-linear regression analysis

Table 4. Plasma PK Parameters for Sisunatovir

Parameter	Study Day	Definition	Method of Determination
AUC _{last}	1, 8	Area under the concentration-time curve from time 0 to the time of last quantifiable concentration	Linear/Log trapezoidal method
AUC _{tau}	1, 4, 8	Area under the concentration time curve from time 0 to the time of the end of the dosing interval (tau), where tau=12 hours	Linear/Log trapezoidal method.
t _{1/2} ^a	1, 8	Terminal half-life	Log _e (2)/k _{el} , where k _{el} is the terminal phase rate constant calculated by a linear regression of the log-linear concentration-time curve
MRT ^a	1, 8	Mean residence time	Day 1: MRT = AUMC _{inf} /AUC _{inf} Day 8: [AUMC _{tau} + tau(AUC _{inf} -AUC _{tau})]/AUC _{tau} where AUMC _{inf} is the area under the first moment curve from zero time to infinity AUMC _{tau} is area under the first moment curve over the dosing interval tau.
V _z /F ^a	1	Apparent volume of distribution	Dose/(AUC _{inf} × k _{el})
CL/F ^a	1, 8	Apparent oral clearance	Dose/AUC _{inf}
R _{ac} ^a	8	Accumulation ratio on AUC _{tau}	AUC ₁₂ (Day 8) /AUC ₁₂ (Day 4)
R _{ac,Cmax} ^a	8	Accumulation ratio on C _{max}	C _{max} (Day 8) /C _{max} (Day 4)
C _{trough}	6, 7, 8	Lowest concentration observed during the dosing interval	Observed directly from data
C _{av}	8	Average concentration at steady state	AUC ₁₂ (Day 8) /12 hours.
V _z /F ^a	8	Apparent volume of distribution at steady state	V _z /F = Dose/(AUC _{tau} × k _{el})
PTR	8	Peak-trough ratio	C _{max} /C _{trough}

a. If data permit.

CCI

CCI

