As of 04 April 2023, there have been no SAEs attributable to sisunatovir and no deaths in the clinical studies. There has been one serious AE of pyrexia reported in the pediatric study (C5241003) in a child hospitalized with RSV infection who received a single dose of sisunatovir. This was considered serious because it prolonged hospitalization, but the SAE was reported as not related to IMP. In Study C5241002 there was 1 SAE of sub-acute myocarditis reported for a participant on placebo; this was considered to be causally related to the challenge virus.

In adults, sisunatovir is slowly absorbed reaching maximum plasma concentrations (T_{max}) at 5-6 hrs with a half-life of 7-10 hrs in healthy participants. Steady-state concentrations were reached after approximately 2 days of dosing and resulting in a 2-4 fold accumulation of exposure. AUC and C_{max} values increased in a greater than dose proportional manner across single and multiple dose studies. Following 5 days of dosing, the variability in PK parameters was high, with %CV ranging from 67.4%-84% for C_{max} and 71.9%-144% for AUC_{12} .

The effect of food on the single dose PK was assessed for the DIC formulation and DPB formulation dispersed in water. For the DIC the extent of systemic exposure to sisunatovir (geometric mean AUC_{inf} under fed and fasted conditions) was 357 and 221 ng•h/mL, respectively, with the between-subject variability being lower under fed conditions (%CV 64.1% compared with 198%). The ratio of fed/fasted was 218% (90% CI 94.2% - 502%) for C_{max} and 190% (90% CI 86.2% – 418%) for AUC_{inf} . It should be noted that the DIC fasted results from C5241001 were lower than typically seen in other studies with 200 mg administered under fasting conditions, resulting in an artificially higher ratio of fed/fasted in this study. For the DPB dispersed in water the extent of systemic exposure to sisunatovir (geometric mean AUC_{inf}) under fed and fasted conditions was 371 and 337 ng•h/mL, respectively, with the between-subject variability being slightly lower under fasted conditions (%CV 49.0% compared with 61.6%). The ratio of fed/fasted was 107.7% (90% CI 78.0% – 148.8%) for C_{max} and 110.0% (90% CI 85.6% – 141.4%) for AUC_{inf} .

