4. STUDY DESIGN

4.1. Overall Design

This is a Phase 1, single-center, open-label and single-arm study to investigate PK, safety and tolerability of 200 mg sisunatovir given as a single dose on Day 1 in a fasted state followed by repeated twice daily doses (200 mg BID, Q12 hours) from Days 4-7 plus 1 morning dose on Day 8 in a fed state in Chinese healthy participants. Approximately 12 participants in total will be included in this study. If a participant discontinues before completing the study, or withdraws for reasons unrelated to the safety of the treatment, the participant may be replaced at the discretion of the investigator upon consultation with the sponsor.

A summary of the schedule of study participation and procedures is provided (see [Schedule of Activities](#)). The study will consist of a Screening visit, a Treatment period of single dosing (Day -1 to Day 3) and multiple dosing (Day 4 to Day 11), and a Follow-up contact. The total duration of participation from the Screening visit to the Follow-up contact will be up to approximately 71 days.

The study period will begin with informed consent from the first participant and will end with the follow up examination of the last participant.

Informed consent to participate in the study will be obtained before initiation of any trial-related activities. Screening examination will be conducted within 28 days before the first study drug administration. Participants will be admitted to the CRU on Day -1, 1 day before the first study drug administration. On Day 1 after fasting for at least 10 hours, all participants will receive a single oral dose of sisunatovir 200 mg at approximately 8:00 am \pm 2 hours in the morning. The participants will be maintained in a fasted state for 4 hours after dosing and undergo serial PK blood sampling for 72 hours post-dose. On Days 4 to 7, participants will receive oral dose of sisunatovir 200 mg twice daily (Q12 hours) in a fed state. On Day 8, the dosing of sisunatovir will be administered under fed condition at approximately 8:00 am \pm 2 hours in the morning. Participants may be discharged on Day 11 after all study procedures are completed.

A follow up contact will be completed at least 28 calendar days and up to 35 calendar days after the last dose of investigational product to capture any potential AEs and concomitant treatments, and to confirm appropriate contraception usage. This follow-up assessment may be conducted via telephone.

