3.2. Secondary Endpoint(s)

The secondary endpoints are additional pharmacokinetics parameters after single and multiple doses of Sisunatovir as detailed in Table 3, as well as safety endpoints described in [Section 3.5](#).

Table 3. Sisunatovir Plasma PK Parameter Definitions

Parameter	Study Day	Definition	Method of Determination
C_{max}	1, 4, 8	Maximum observed concentration	Observed directly from data
T_{max}	1, 4, 8	Time to reach maximum concentration	Observed directly from data
AUC_{inf}^a	1, 8	Area under the concentration-time curve from time 0 to infinity	$AUC_{last} + (C_{last}/k_{el})$, where C_{last} is the predicted plasma concentration at the last quantifiable time point estimated from the log-linear regression analysis
AUC_{last}	1, 8	Area under the concentration-time curve from time 0 to the time of last quantifiable concentration	Linear/Log trapezoidal method
AUC_{tau}	1, 4, 8	Area under the concentration time curve from time 0 to the time of the end of the dosing interval (τ), where $\tau=12$ hours	Linear/Log trapezoidal method.
$t_{1/2}^a$	1, 8	Terminal half-life	$\log_e(2)/k_{el}$, where k_{el} is the terminal phase rate constant calculated by a linear regression of the log-linear concentration-time curve
MRT^a	1, 8	Mean residence time	Day 1: $MRT = AUMC_{inf}/AUC_{inf}$ Day 8: $[AUMC_{tau} + \tau(AUC_{inf} - AUC_{tau})]/AUC_{tau}$ where $AUMC_{inf}$ is the area under the first moment curve from zero time to infinity $AUMC_{tau}$ is area under the first moment curve over the dosing interval τ .

Table 3. Sisunatovir Plasma PK Parameter Definitions

Parameter	Study Day	Definition	Method of Determination
V_z/F^a	1	Apparent volume of distribution	$Dose/(AUC_{inf} \times k_{el})$
CL/F^a	1, 8	Apparent oral clearance	$Dose/AUC_{inf}$
R_{ac}^a	8	Accumulation ratio on AUC_{tau}	$AUC_{12}(\text{Day 8})/AUC_{12}(\text{Day 4})$
$R_{ac,C_{max}}^a$	8	Accumulation ratio on C_{max}	$C_{max}(\text{Day 8})/C_{max}(\text{Day 4})$
C_{trough}	6, 7, 8	Lowest concentration observed during the dosing interval	Observed directly from data
C_{av}	8	Average concentration at steady state	$AUC_{12}(\text{Day 8})/12 \text{ hours.}$
V_z/F^a	8	Apparent volume of distribution at steady state	$V_z/F = Dose/(AUC_{tau} \times k_{el})$
PTR	8	Peak-trough ratio	C_{max}/C_{trough}

a. If data permit.

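### Day 8 CL/F is defined as Dose/AUCinf, an area that includes drug left from earlier doses; under a linear one-compartment model it understates clearance by about 40–50%

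*Protocol*

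**What the plan says.** Protocol Section 9.3.1.2, Table 4, has one CL/F row covering both profile days: "1, 8 Apparent oral clearance Dose/AUC", with subscript inf. SAP Section 3.2, Table 3, repeats it: the row "Apparent oral clearance" is also for Days 1 and 8 and is also Dose/AUCinf. AUCinf, listed for the same two days, is "Area under the concentration-time curve from time 0 to infinity", with no correction for drug already present at the Day 8 dose.

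Other Day 8 parameters in the same tables are treated differently:

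- Vz/F has two rows. Day 1 is Dose/(AUCinf × kel). Day 8, labelled "Apparent volume of distribution at steady state", is Dose/(AUCtau × kel).
- MRT has a separate Day 8 formula with AUCtau as denominator.
- Cav on Day 8 is AUC12 divided by 12 hours.

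SAP Section 2.1 declares no modifications to the protocol analysis. The footnote on data availability attached to CL/F governs whether it is calculated, not how.

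**The concern.** Dose/AUCinf is apparent clearance only when the whole area comes from that one dose. On Day 8 it does not. The multiple-dose course runs "from Days 4-7 plus 1 morning dose on Day 8", so the Day 8 curve contains what is left of eight earlier 200 mg doses. One dose is divided by an area that several doses produced, and the quotient is too small.

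Day 8 CL/F is a listed secondary endpoint, summarized by study day in a study meant to support registration in China. The summary table would show clearance well below the Day 1 value even if nothing had changed. That artefact could be taken for something real. Day 1 is fasted and Day 8 fed, and Protocol Section 4.2 says the design may help to assess a breakfast effect. The protocol also describes sisunatovir as mainly metabolized by CYP3A4 (Section 2.2.2) and as a moderate CYP3A4 inhibitor (Section 2.2.4), so a fall in clearance on repeated dosing would look plausible.

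**Working it through.** The documents state no value for CL/F, so there is no planned figure to reproduce. The check has a model-free part and a sizing part.

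**1. Internal consistency (no model).** By definition CL/F = kel × Vz/F. Using the tables' own formulas:

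- Day 1: kel × Dose/(AUCinf × kel) = Dose/AUCinf. This equals the tabulated CL/F.
- Day 8: kel × Dose/(AUCtau × kel) = Dose/AUCtau. The tabulated CL/F is Dose/AUCinf, a different number.

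**2. Direction (no model).** On Day 8, AUCinf = AUCtau + the area from 12 h to infinity. The second term is positive whenever drug remains at 12 h, so Dose/AUCinf is below Dose/AUCtau. At steady state the amount eliminated in one interval equals F × Dose, so Dose/AUCtau is the apparent clearance averaged over the interval.

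**3. Size (model).** Inputs:

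- Interval: "where tau=12 hours" (Protocol Table 4).
- Doses: 4 days × 2 + 1 = 9 (Protocol Section 4.1).
- Tmax and half-life: "at 5-6 hrs with a half-life of 7-10 hrs in healthy participants" (Protocol Section 2.2.4).
- Assumed: one compartment, first-order absorption, linear kinetics, with ka solved from the single-dose Tmax.

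Formulas, with k = ln 2/t½:

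- Tmax = ln(ka/k)/(ka − k), solved for ka.
- Single-dose curve, in units of F·Dose/V: C(t) = ka/(ka − k) × (e^(−kt) − e^(−ka·t)).
- Day 8 AUCinf = the sum over i = 0 to 8 of ka/(ka − k) × (e^(−12ki)/k − e^(−12ka·i)/ka).
- Day 8 AUCtau: the nine superposed curves integrated from 0 to 12 h.
- Reported CL/F as a share of true CL/F = AUCtau/AUCinf.

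Example, t½ 10 h and Tmax 5 h: k = 0.0693 and ka = 0.438. With the carry-over sum taken to its limit, k × AUCinf = 0.0693 × 1.188 × [1/(0.0693 × 0.5647) − 1/(0.438 × 0.9948)] ≈ 1.915. Since k × AUCtau ≈ 1, the understatement is 1 − 1/1.915 = 47.8%.

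| t½ (h) | Tmax (h) | ka (1/h) | AUCinf/AUCtau | Reported/true CL/F | Understated by |
|---|---|---|---|---|---|
| 7 | 5 | 0.354 | 1.60 | 0.624 | 37.6% |
| 7 | 6 | 0.260 | 1.68 | 0.595 | 40.5% |
| 8.5 | 5 | 0.399 | 1.75 | 0.570 | 43.0% |
| 8.5 | 6 | 0.297 | 1.82 | 0.550 | 45.0% |
| 10 | 5 | 0.438 | 1.92 | 0.522 | 47.8% |
| 10 | 6 | 0.329 | 1.97 | 0.507 | 49.3% |

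Applying the linear/log trapezoidal rule at the Protocol Table 2 sampling times gives the same percentages to within 0.1 point. In all six cases k × AUCtau is 0.999 to 1.000, so Dose/AUCtau recovers the true value to within 0.1%.

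**4. Sensitivity to absorption.**

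- Instantaneous absorption: the error is 2^(−12/t½), which is 30.5% at 7 h, 37.6% at 8.5 h and 43.5% at 10 h.
- Very slow absorption (ka solved from a steady-state Tmax of 5 h, t½ 8.5–10 h): about 60%.

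**5. Accumulation as a cross-check.** The six cases above give a Day 8/Day 4 AUCtau ratio of 1.7 to 2.2, at the low end of the protocol's statement, "resulting in a 2-4 fold accumulation of exposure". The very slow absorption case gives 3.7 to 3.8.

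**The case against.** The strongest reply concerns consequence. Day 8 CL/F is secondary, the study tests no hypothesis, and all PK parameters are only listed and summarized. Day 8 AUCtau will be reported and every participant is planned to receive 200 mg, so a reader could recompute the right value. No primary endpoint changes. All of this is true and limits the harm, but it does not justify prespecifying an endpoint that its own formula makes wrong.

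The size is also open to challenge. Protocol Section 2.2.4 reports greater than dose-proportional exposure, so a linear model is an approximation. Nor can the documented accumulation be turned directly into a larger error. Under instantaneous absorption with a 7–10 h half-life, accumulation would be only 1/(1 − 2^(−12/7)) = 1.44 to 1.77, so 2–4 fold does not fit that model. The objection stands as to size. It does not touch the direction or the remedy, because the steady-state mass balance does not require linearity.

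Finally, CL/F contains F, and Day 1 is fasted while Day 8 is fed, so even the corrected values need not agree. That also stands. With the fed/fasted AUCinf ratio of 110.0% reported for the powder blend in water, unchanged clearance would give a Day 8/Day 1 CL/F ratio of 1/1.10 = 0.91. The current formula would give 0.91 × 0.507 to 0.91 × 0.624, or 0.46 to 0.57. The artefact would swamp the difference of interest.

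**Conclusion.** The concern holds. Both documents define Day 8 CL/F with the wrong area, nothing elsewhere corrects it, and the definition contradicts the Day 8 Vz/F row in the same tables. That Day 8 clearance is understated follows from the definitions and from steady state, which Protocol Section 2.2.4 says is reached after about 2 days of dosing. The best estimate of the size is 38% to 49%, conditional on linear one-compartment kinetics with the protocol's half-life and Tmax; across absorption assumptions it is roughly 30% to 60%. The error is confined to one secondary endpoint. Day 1 CL/F, Cmax, the AUCs, Vz/F and Cav are not affected. It should be corrected before the parameters are derived.

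**What to change.** In SAP Table 3 and Protocol Table 4, split the CL/F row as the Vz/F row already is:

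- Day 1: CL/F = Dose/AUCinf.
- Day 8: CL/F = Dose/AUCtau, labelled as apparent clearance at steady state.

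Keep AUCinf on Day 8, since it is a listed endpoint and the Day 8 MRT formula needs it. Record the change in SAP Section 2.1. Protocol Section 9 lets the SAP modify the protocol's outline and asks for an amendment only for major changes to the primary endpoints, so the SAP can carry the correction; the protocol table should be aligned when it is next amended.

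The cost is one table row. No sample, visit or new parameter is needed, because Day 8 AUCtau is already a primary endpoint. Day 8 CL/F would also no longer depend on extrapolation to infinity, so it could be calculated in participants whose terminal slope cannot be estimated.
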